Saline is administered for blinding purposes. To maintain the observer-blind design of the study, the roles and responsibilities of “blinded” and “unblinded” team members will be defined. After vaccination, safety assessments and study related procedures and monitoring thereof must be performed by “blinded” team members.

After each vaccination, all subjects will remain under medical supervision at the study site for at least 30 minutes to be monitored and evaluated for adverse events (AEs). The parent/legal guardian or a designated person (e.g., caregiver) will be instructed on the measurement of local and systemic solicited adverse events, including body temperature (preferably oral), and on the completion of the Subject Diary cards. A Subject Diary will be used to describe solicited local and systemic adverse events that may occur post-vaccination from Day 1 through Day 7 (all subjects) and Day 29 through Day 35 (“not previously vaccinated” subjects). Any adverse event and concomitant medication use after vaccination will be collected from Day 1 to Day 22 during the Day 22 clinic visit (“previously vaccinated” subjects) and from Day 1 to Day 50, during the Day 29 and Day 50 clinic visit (“not “previously vaccinated” subjects). Information collected at these visits will be documented in the subject’s source records and captured in the electronic Case Report Form (eCRF). All subjects will also receive an ILI booklet on Day 1, and they (or the parent/legal guardian or a designated person) will be instructed to measure their body temperature using the thermometer provided, starting from onset day of protocol defined ILI to the day they come in to the clinic for the Nasopharyngeal (NP) swab collection. The ILI booklet will be returned at the time of their NP visit.

During the remaining follow-up phase of the study (up to Day 181 for “previously vaccinated” subjects or Day 209 for “not previously vaccinated” subjects, or until the end of influenza season, whichever is longer), safety data including adverse events leading to withdrawal, New Onset of Chronic Diseases (NOCDs), Serious Adverse Events (SAEs), ILIs and all medications use related to these events will be captured via safety phone calls as described in the time and events table.

Name of Sponsor:	Protocol number:	Generic name of study vaccine(s):
Seqirus UK Ltd	V130_12	Cell-Based Quadrivalent Subunit Influenza Virus Vaccine (QIVc) Meningococcal (Groups A, C, Y, W-135) Conjugate Vaccine (Men ACWY)

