After randomization, all subjects will receive a dose of 0.5 mL of study vaccine to which they were assigned (QIVc or non-influenza comparator vaccine) on Day 1, administered intramuscularly in the deltoid muscle, preferably of the non-dominant arm. For those subjects who are “not previously vaccinated” a second administration will follow on Day 29, as presented below:

Table 3-2: Vaccination Schedule

Subjects	QIVc Group	Comparator Group
“previously vaccinated” ≥ 2 years to < 9 years of age, and ≥ 9 years to < 18 years of age	Day 1: QIVc	Day 1: Men ACWY
“not previously vaccinated” ≥ 2 years to < 9 years of age	Day 1: QIVc Day 29: QIVc	Day 1: Men ACWY Day 29: Saline

To maintain the observer-blind design of the study, the roles and responsibilities of “blinded” and “unblinded” team members will be defined. After vaccination, safety assessments and study related procedures and monitoring thereof must be performed by “blinded” team members.

This study is planned for at least three influenza seasons. Laboratory confirmed influenza cases will be reviewed on a regular basis (blinded review). If decided by the Sponsor, and after observing at least 50% of planned events meeting the co-primary endpoint, interim analyses for efficacy may be performed for evaluation by a DMC.

Study Definition of Influenza-Like-Illness and Influenza Case

An Influenza Like Illness (ILI) Case is defined as follows: The Centers for Disease Control and Prevention (CDC) criteria ILI is modified for young children for the purposes of this study to include additional symptoms): fever of $\geq 100.0^{\circ}\text{F}$ / $\geq 37.8^{\circ}\text{C}$ along with any of the following: cough, sore throat, nasal congestion, or rhinorrhea.

The ILI onset day is defined as the first day that the subject meets the primary protocol defined ILI.

The ILI end date is defined as the date the last symptom resolves.

A new ILI episode will only be taken into account after resolution of the previous one, as judged by the investigator (suggested interval between two ILI episodes is 14 symptom free days).

A detailed schedule and listing of procedures are shown in the Time and Events Tables 3-7 (see [protocol synopsis](#)).

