8.2.1 Safety Data

For unsolicited adverse events, the entire study period will be divided into the following intervals: Day 1 to Day 22, Day 23 to Day 181 in “previously vaccinated” subjects and Day 1 to Day 50, Day 51 to Day 209 in “not previously vaccinated” subjects.

For solicited adverse events, the solicited study period 30 min - Day 7 after each vaccination will be divided into: 30 min and Day 1-7 (without the 30-minute interval).

No imputation of missing solicited or unsolicited AEs will be used. The percentage of subjects with missing solicited AE assessments and missing safety phone calls or safety assessment, including subjects who discontinued the study, will be reported for each time.

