The duration is missing if one of the dates is missing or incomplete.

Solicited Adverse Events

For details, see [Section 13.2](#).

Unsolicited Adverse Events

All adverse events will be characterized according to the date of occurrence related to the vaccination phase as follows:

- **Emergence before vaccination phase:** start date before the first date of injection of study vaccine.
- **Emergence during vaccination phase:** start date on or after the first date of injection of study vaccine or, adverse event increase in severity including to “serious” adverse event.

If the start date is equal to the first date of injection then a “timing” variable (“On injection day, before injection” / “On injection day, after injection”) will be used to define whether the adverse event occurred before or after the injection.

If there are several vaccinations, the adverse event will be associated with the most recent vaccination.

If an adverse event start date is missing or unknown, the adverse event will be considered as emergent.

When start and/or end dates of an adverse event are only partially known, adverse events will be categorized as emergent before, during, or after vaccination phase using the following rules:

- If the partial end date is before (<) the first study vaccination (i.e., year or year & month is/are before the first study vaccination year or year & month) then the adverse event is emergent before vaccination phase.
- If the partial start date is equal or after (\geq) the first study vaccination (i.e., year or year & month is/are after or the same as the first study injection year or year & month) then the adverse event is emergent during vaccination phase.

The **maximum event severity** is the greatest severity associated with a preferred term for a reported adverse event according to the following order: Mild < Moderate < Severe. Unknown/ Missing severity is considered as severe (except for the definition of emergence).

Multiple AEs with the same PT for the same subject are counted only once.

Vaccination-related Adverse Events are those for which the cause has been evaluated by the investigator, and recorded either as possibly related, probably related or unknown/missing.

Safety Laboratory Data

Not applicable.

Pre-study, Concomitant and Post-Study Medications

A **pre-study medication** is a medication used only before the first study vaccination (i.e. medication end date < first study vaccination date).

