Injection site pain and systemic AEs (except fever) occurring for the 7 days including each vaccination will be summarized according to “mild”, “moderate” or “severe”.

Each solicited local and systemic AE will also be further summarized as “none” versus “any”.

The analyses will encompass summaries of the data on five levels:

1. Daily reports of subjects with solicited adverse events.
2. Time of first onset of solicited adverse events (excluding 30 min measurement).
3. Solicited adverse events, maximum event severity by event on Day 1-7 without 30 min.
4. Duration of solicited adverse events.

5. Solicited adverse events and indicators of solicited adverse events, occurrence of at least one event by category (local, systemic) and interval Day 1-7 without 30 min.

For each of the time points or time intervals presented in the summaries, only subjects with at least one plausible observation (i.e., any non-missing values but excluding “Not done/unknown” and implausible values) for the solicited adverse events in the interval of interest will be considered. Subjects without plausible data (i.e. missing values or reported as “Not done/unknown” and implausible values) will be removed from the denominator to prevent a downward bias (towards zero).

Level 1: Daily reports of solicited adverse event

For each of the time points only subjects with at least one plausible observation (i.e., any non-missing values but excluding “Not done/unknown” and implausible values) for the solicited adverse event in the interval of interest will be considered. Subjects without plausible data (i.e. missing values or reported as “Not done/unknown” and implausible values) will be removed from the denominator in order to prevent a downward bias (towards zero). Data collected will be summarized (frequencies and percentages of subjects) by vaccine group, solicited adverse event, vaccination number and time point.

Level 2: Time of first onset of solicited adverse events

The time of first onset is defined, for each subject, for each solicited adverse event, as the time point on which the respective solicited adverse event first occurred. For erythema, ecchymosis and induration two thresholds will be used: ≥ 1 mm and ≥ 25 mm for children older than 6 years or ≥ 1 mm and ≥ 9 mm for children aged 6 and below.

Table 13.2-2: Example for Time to First Onset of Solicited Adverse Events

Vaccination	Subject Number	Day 1 ^a	Day 2	Day 3	Day 4	...	Day 7
1	001	None	Severe	Moderate	None	...	None

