The number of days with the adverse event is defined irrespective of severity. This means at least ‘mild’ solicited adverse event that are assessed qualitatively. For erythema, ecchymosis and induration two thresholds will be used: ≥ 1 mm and ≥ 25 mm for children older than 6 years or ≥ 1 mm and ≥ 9 mm for children aged 6 years and below. If a solicited adverse event continues beyond Day 7, the period after Day 7 is added as an unsolicited adverse event.

The frequency distribution of the number of days will be provided in a summary table by vaccine and by adverse event.

Level 5: Solicited adverse events, occurrence of at least one event by category (local, systemic) and interval.

The **occurrence of at least one solicited adverse event** is defined as “any” for a subject if he/she reports greater than “none” for the respective event and “none” otherwise. For erythema, ecchymosis and induration two thresholds will be used for an event: ≥ 1 mm and ≥ 25 mm for children older than 6 years or ≥ 1 mm and ≥ 9 mm for children aged 6 years and below. The occurrence of at least one solicited adverse event (i.e., none versus any) will be summarized by category (i.e., local, systemic, any), by vaccine group, by vaccination (after each vaccination and after any vaccination) and by time interval.

Medications to treat or prevent pain or fever will be summarized by frequencies and percentages of subjects reporting use of the medications by interval 30 min, Day 1 – 7 (excluding 30 minutes after vaccination).

For details please refer to [section 7.1.1 of the protocol](#).

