13.3 Unsolicited Adverse Events

The first-line analysis will use unsolicited adverse event data from all reporting sources combined. A second-line analysis will encompass the analysis of unsolicited adverse events by source.

All the unsolicited adverse events occurring during the study, judged either as probably related, possibly related, or not related to vaccination by the investigator, will be recorded. The original verbatim terms used by investigators to identify adverse events in the case report forms (CRFs) will be mapped to preferred terms using the MedDRA dictionary. The unsolicited adverse events will then be grouped by MedDRA preferred

terms into frequency tables according to system organ class. Adverse events judged by the investigator as at least possibly related to study vaccine will be summarized by vaccine group, according to system organ class and preferred term within system organ class. When an unsolicited adverse event occurs more than once for a subject, the maximal severity and strongest relationship to the vaccine group will be counted.

Only vaccine-emergent adverse events (see [protocol section 8.7](#) for definition) will be analyzed, i.e., excluding those after a subject has given informed consent but before vaccination. The selection of unsolicited adverse events and the assignment to time intervals will be done by day of onset and not by days ongoing/persisting.

The summaries will be presented by period of onset and will include frequency distributions of the different adverse events:

Previously vaccinated subjects:

- Onset between Day 1 and Day 22
- Onset between Day 23 and Day 181

Not previously vaccinated subjects:

- Onset between Day 1 and Day 50
- Onset between Day 51 and Day 209

The analysis of unsolicited adverse events comprises the following categories:

- Any unsolicited adverse event
- Possibly or probably related unsolicited adverse events
- Unsolicited adverse events leading to death
- Serious adverse events
- Possibly or probably related serious adverse event
- Unsolicited adverse events leading to premature withdrawal from study
- Unsolicited adverse events leading to dose reduction, interruption or delay in study vaccination
- Medically attended adverse events

- Unsolicited adverse events leading to new onset of chronic disease (NOCD)

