18. LAYOUT SPECIFICATIONS FOR TABLES, LISTINGS AND FIGURES

All TLFs will include a header with the following components, e.g.:

Seqirus Inc. Final Report: Study 130_12	Vaccine: QIVc Phase III/IV, Subjects ≥ 2 years to < 18 Years
--	--

In all tables, listings and figures, vaccine groups will be labeled as “QIVc”, “Vaccine Comparator”.

The mock-up catalogue will be used during programming.

Since all TLFs will be produced using SAS[®], the output actually generated may slightly differ from the mock-ups presented in the study specific mock-up catalogue.

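### In the two-dose stratum, unsolicited adverse events are pooled across a MenACWY-controlled and a saline-controlled period; a descriptive split at dose 2 and a footnote should be added

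*SAP*

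**What the plan says.** - **Regimen.** SAP Section 3, Table 3-2, gives the comparator arm of the not previously vaccinated stratum "Day 1: Men ACWY Day 29: Saline". The QIVc arm receives QIVc on both days. The protocol synopsis (Study Design) explains that "Saline is administered for blinding purposes". No other stratum receives saline.
- **Unsolicited events.** For this stratum SAP 13.3 lists "Onset between Day 1 and Day 50" and then Day 51-209. SAP 8.2.1 has the same cut, "Day 1 to Day 50, Day 51 to Day 209 in" not previously vaccinated subjects, and Protocol 8.4.3.1.3 agrees. None of them divides the early interval at Day 29.
- **Attribution to dose.** SAP 8.6 states: "If there are several vaccinations, the adverse event will be associated with the most recent vaccination". SAP 13.3 plans no table that uses this link.
- **Solicited events.** SAP 13.2 reports daily data "by vaccine group, solicited adverse event, vaccination number and time point" (Level 1), shows separate rows for vaccination 1 and 2 in the Level 2 mock-up, and reports occurrence "by vaccination (after each vaccination and after any vaccination) and by time interval" (Level 5). Protocol 8.4.3.1.2 also treats Day 29-35 as its own period.
- **Labels.** SAP 18: "In all tables, listings and figures, vaccine groups will be labeled as" *QIVc* and *Vaccine Comparator*. It mentions no footnote for saline.

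**The concern.** From Day 29 to Day 50 the comparator child has most recently had saline; before that, an active vaccine. A single Day 1-50 percentage per arm mixes two different comparisons and shows neither. Someone asking how the second QIVc dose compares with an inert injection for unsolicited events finds no planned table that answers it, although the variable needed is already derived.

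The counting rules add to this. Under SAP 8.6 repeated events with the same preferred term count once per child, and SAP 13.3 keeps only the maximal severity. A child with the same event after both doses therefore counts once in Day 1-50, and the dose-2 recurrence drops out of the table. Solicited events that last beyond Day 7 are reported as unsolicited (SAP 13.4), so they enter the unsplit tables as well.

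For solicited events the matter is smaller. A dose-2 row headed *Vaccine Comparator* could be read as reactogenicity of a vaccine when the injection was saline. The rows for any vaccination combine MenACWY and saline without saying so.

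**Working it through.** **1. Size of the stratum and window.** SAP Table 3-1 plans 1,022 to 1,430 not previously vaccinated children per arm. As a share of the trial: 2,044/7,692 = 27% to 2,860/7,692 = 37%. Nominally, Day 29-50 is 22 of 50 days, 22/50 = 44%. Visit windows (Day 29 ±3, Day 50 −1 to +4) shift this per child.

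**2. What pooling does.** Let q1, q2 be the risks of at least one unsolicited event in the QIVc arm before and after dose 2, and c1, c2 those in the comparator arm. If the two periods are independent within a child, the Day 1-50 risk is 1 − (1 − r1)(1 − r2), and the pooled difference splits into

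(1 − q1)(q2 − c2) + (q1 − c1)(1 − c2).

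The dose-2 contrast is always shrunk by the factor 1 − q1. The dose-1 contrast against MenACWY is then added, with either sign.

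**3. Numbers.** The documents give no event rates, so these are assumptions: QIVc 20% in each period, saline 15%. The dose-2 difference is 20 − 15 = 5 points throughout.

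| Assumed MenACWY risk, dose 1 | QIVc, Day 1-50 | Comparator, Day 1-50 | Pooled difference |
|---|---|---|---|
| 15% | 1 − 0.80×0.80 = 36.0% | 1 − 0.85×0.85 = 27.75% | +8.25 points |
| 20% | 36.0% | 1 − 0.80×0.85 = 32.0% | +4.0 points |
| 25% | 36.0% | 1 − 0.75×0.85 = 36.25% | −0.25 points |

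In the middle row the risk ratio falls from 20/15 = 1.33 to 36/32 = 1.125.

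**4. A second set of assumed rates.** Background 10% per period, QIVc and MenACWY each add 5 points, saline adds none. Dose 2: 15% versus 10%, ratio 1.50. Pooled: 1 − 0.85×0.85 = 27.75% versus 1 − 0.85×0.90 = 23.5%, a difference of 4.25 points, ratio 1.18. If MenACWY adds 10 points instead, the comparator is 1 − 0.80×0.90 = 28.0% and the ratio is 0.99.

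**5. Precision of the split.** In the 20% versus 15% case the standard error of the dose-2 difference is √[(0.16 + 0.1275)/n], which is 1.68 points at n = 1,022 and 1.42 at n = 1,430. The 5-point difference is thus about 3.0 to 3.5 standard errors, if every child receives dose 2.

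**6. Rare events.** The plan's own safety figure reproduces: 1 − (1 − 1/1,000)^2,674 = 93.1%. With 1,022 to 1,430 children the same formula gives 64.0% to 76.1% for a 1-in-1,000 event. With 10% loss (920 to 1,287) it gives 60.2% to 72.4%. The dose-2 window is informative for common events and limited for rare ones.

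**The case against.** Several counter-arguments are sound and limit the point.

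- **The endpoint is Day 1-50.** Protocol 8.1.2.1 and SAP 2.2.6 both define the unsolicited endpoint this way, so SAP 13.3 implements it correctly. A reader might infer that the pooled table leaves the tolerability objective unanswered. The documents do not support that: what is missing is a supplementary breakdown.
- **Solicited data are separated by dose.** A reader might infer that the whole saline-controlled safety comparison is hidden. For reactogenicity it is not: SAP 13.2 shows it by vaccination, and SAP 8.5 isolates the stratum by previous vaccination status. The arm label is defensible, because Table 3-2 defines the regimen behind it; a footnote is enough.
- **The window is not a clean placebo control.** Saline was given for blinding. Children were randomised to regimens, dose 2 depends on what happened after dose 1 (Protocol 4.4), and late events from the Day 1 injection can fall in the window.
- **Full cancellation depends on chosen rates.** It appears only when MenACWY is assumed more reactogenic than QIVc by about as much as saline is less so. With equal active risks the loss is 1 point in 5. The periods are also unlikely to be independent within a child, and safety analyses carry no hypothesis test.
- **Shells and listings exist.** SAP 17 and 18 defer to a table list and mock-up catalogue that are not part of the documents, and onset dates allow a later split.

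What remains is that no text plans the split. SAP 8.5 promises safety analyses by time period, and Protocol 8.3.6 leaves those periods to the SAP, but the only unsolicited periods the SAP defines are the pooled ones. Subgrouping by vaccination status separates the stratum, not the dose. Listings give no comparative rates.

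**Conclusion.** The point holds as a reporting gap in the unsolicited-event tables of one stratum. Pooling over Day 1-50 shrinks any dose-2 excess of QIVc over saline and adds the dose-1 contrast with MenACWY. Under the equal-risk assumption 5 points become 4. Across assumed MenACWY risks of 15% to 25% the pooled difference runs from +8.25 to −0.25 points while the dose-2 difference stays at 5, so the pooled figure cannot be read as the dose-2 contrast. These rates are illustrative and rest on independence between periods; they show the mechanism and do not predict the trial's result. For solicited events the issue is labelling only. Safety is descriptive, so no efficacy conclusion, error rate or defined endpoint changes. Because the split is cheap and concerns a stated objective, it should be made.

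**What to change.** 1. In SAP 13.3 (and 8.2.1) keep Day 1-50 as the endpoint summary. For not previously vaccinated subjects add two descriptive sub-periods using the SAP 8.6 attribution: dose 1 to before dose 2 (QIVc versus MenACWY), and dose 2 to the Day 50 visit (QIVc versus saline).
2. Use subjects who received dose 2 as the denominator of the second sub-period. State that, under the 8.6 rule, events in a child who never receives dose 2 stay with dose 1.
3. Count repeated preferred terms once within each sub-period, so that a recurrence after dose 2 is visible.
4. In SAP 18 require a footnote on dose-2 safety tables, solicited and unsolicited, that the comparator injection was saline, and on tables for any vaccination that the comparator regimen was MenACWY then saline.
5. State that the dose-2 window is descriptive, is conditional on receiving dose 2, and may include late events from the Day 1 injection.

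The cost is SAP wording, a few table columns from a variable already derived, and footnotes. No new data are needed.

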13.4 Combined Solicited and Unsolicited Adverse Events

Solicited adverse events continuing beyond Day 7 will be reported as an unsolicited AE by the PI and subsequently coded by MedDRA and combined with the unsolicited adverse events as routinely collected beyond Day 7.

A summary of subjects with all combined solicited and unsolicited adverse events will be provided using preferred MedDRA terms for solicited adverse events.

Out of window solicited and unsolicited adverse events and reason for exclusion of these AEs from the analysis of the safety data will be presented as separate listings.

